Appendix 8 Hemophilia Joint Health Score (HJHS)

Subject ID #: _____

Name of physiotherapist: _____

Assessment #: _____

Date: _____

Time: _____

yyyy / mm / dd

Hemophilia Joint Health Score 2.1 – Summary Score Sheet

	Left Elbow		Right Elbow		Left Knee		Right Knee		Left Ankle		Right Ankle	
Swelling		NE		NE		NE		NE		NE		NE
Duration (swelling)		NE		NE		NE		NE		NE		NE
Muscle Atrophy		NE		NE		NE		NE		NE		NE
Crepitus on motion		NE		NE		NE		NE		NE		NE
Flexion loss		NE		NE		NE		NE		NE		NE
Extension loss		NE		NE		NE		NE		NE		NE
Joint pain		NE		NE		NE		NE		NE		NE
Strength		NE		NE		NE		NE		NE		NE
Joint Total												

Sum of Joint Totals

NE = Non-Evaluable

Global Gait Score

(NE included in Gait items)

HJHS Total Score

Swelling

0 = None
1 = Mild
2 = Moderate
3 = Severe

Crepitus on Motion

0 = None
1 = Mild
2 = Severe

Strength (Using the Daniels & Worthingham's scale)

Within available ROM
0 = Holds test position against gravity within maximum resistance (gr. 5)
1 = Holds test position against gravity within moderate resistance (but breaks with maximal resistance) (gr. 4)
2 = Holds test position with minimal resistance (gr. 3+) or holds test position against gravity (gr. 3)
3 = Able to partially complete ROM against gravity (gr.3-/2+) Or able to move through ROM gravity eliminated (gr. 2) Or through partial ROM gravity eliminated (gr. 2-)
4 = Trace (gr.1) or no muscle contraction (gr. 0)
NE = Non-Evaluable

Duration

0 = No swelling
Or < 6 months
1 = ≥ 6 months

Flexion Loss

0 = < 5°
1 = 5° - 10°
2 = 11° - 20°
3 = > 20°

Muscle Atrophy

0 = None
1 = Mild
2 = Severe

Extension Loss

(from hyperextension)
0 = < 5°
1 = 5° - 10°
2 = 11° - 20°
3 = > 20°

Global Gait

0 = All skills are within normal limits
1 = One skill is not within normal limits
2 = Two skills are not within normal limits
3 = Three skills are not within normal limits
4 = No skills are within normal limits
NE = Non-Evaluable

Joint Pain

0 = No pain through active range of motion
1 = No pain through active range; only pain on gentle overpressure or palpation
2 = Pain through active range

NOTE: there is an accompanying instruction manual and worksheets that are required when administering the HJHS

Appendix 8 Hemophilia Joint Health Score (HJHS) (cont.)

General comments:

The HJHS is designed for use by physiotherapists. In order to maintain the precision and validity of the tool (score), the developers of the tool strongly recommend that the tool be used by a physiotherapist/healthcare professionals who have hemophilia-related expertise/experience and have been trained in the use of clinical measures, musculoskeletal assessment and specifically administration of the HJHS.

It is essential for the physiotherapist to possess the requires expertise and skills necessary to use anthropometric measures such as muscle testing and range of motion /goniometry, as well as posture & gait assessment prior to performing the evaluation (HJHS).

Appendix 9

Guidelines for Dosing and Monitoring Bypassing Agents for Patients on Emicizumab

The use of bypassing agents is not expected in hemophilia A patients without inhibitors. For completeness, this appendix includes guidelines provided for treatment of breakthrough bleeds in patients with inhibitors. Careful consideration of the risks and potential benefits is advised when combining emicizumab, factor VIII (FVIII), and bypassing agent.

Drugs intended to control bleeds, including bypassing agents, should be used at the lowest dose expected to achieve hemostasis. Given that circulating emicizumab may increase patients' coagulation potential, the doses required to achieve hemostasis may be lower than the FVIII or bypassing agent doses used prior to starting the study.

Caution should be taken for patients who are using recombinant activated factor VII (rFVIIa [e.g., consideration of using no more than 90 µg/kg of rFVIIa as an initial dose]).

Use of activated prothrombin complex concentrate (aPCC) in combination with emicizumab should be avoided completely in patients who have the option of using other bypassing agents to treat bleeds. In the event that aPCC is the only available bypassing agent, the lowest dose expected to achieve hemostasis should be prescribed, with no more than 50 units/kg of aPCC to be administered as an initial dose.

Other bypassing agents (e.g., Byclot[®]) should be avoided. In cases where such agents are the only available bypassing agent, the lowest dose expected to achieve hemostasis should be prescribed, with no more than the lowest dose described in the prescribing information to be administered as an initial dose (e.g., no more than 60 µg/kg of Byclot[®]).

Exact dose and schedule of bypassing agents should be discussed with patients at the beginning and throughout the study. Repeated dosing of rFVIIa, aPCC, or other bypassing agents should be performed only under medical supervision, which includes laboratory monitoring by additional local and central laboratory assessments, and consideration should be given to verifying bleeds prior to repeated dosing.

Caution should be taken if anti-fibrinolytics are used in conjunction with rFVIIa in patients receiving emicizumab. The use of anti-fibrinolytics in conjunction with aPCC or Byclot[®] is prohibited.

MONITORING:

In the event of a bleed treated with bypassing agents, the following local laboratory tests will be performed within 24–48 hours of initial bypassing agent use so the investigator may monitor for potential thromboembolic events and thrombotic microangiopathy: platelet count, serum creatinine, LDH, and peripheral blood smear analysis to evaluate for schistocytes. A plasma sample should also be provided for local (first aliquot) and

Appendix 9

Guidelines for Dosing and Monitoring Bypassing Agents for Patients on Emicizumab (cont.)

central (second aliquot) laboratory monitoring of prothrombin fragment 1+2, fibrinogen, and D-dimer. If the test for prothrombin fragment 1+2 is not available at the site, the sample should be sent to the local reference laboratory, if available and if the results from the local reference laboratory can be obtained within a reasonable timeframe to allow for decision making. For patients who require multiple doses of bypassing agents, laboratory monitoring should be performed every 24–48 hours thereafter until 24–48 hours following the last dose of bypassing agents administered to treat a given bleed. If applicable, laboratory results should be recorded in the unscheduled visit electronic Case Report Forms (eCRFs).

Appendix 10

Anaphylaxis Precautions

These guidelines are intended as a reference and should not supersede pertinent local or institutional standard operating procedures.

REQUIRED EQUIPMENT AND MEDICATION

The following equipment and medication are needed in the event of a suspected anaphylactic reaction during study treatment infusion:

- Monitoring devices: ECG monitor, blood pressure monitor, oxygen saturation monitor, and thermometer
- Oxygen
- Epinephrine for subcutaneous, intramuscular, intravenous, and/or endotracheal administration in accordance with institutional guidelines
- Antihistamines
- Corticosteroids
- Intravenous infusion solutions, tubing, catheters, and tape

PROCEDURES

In the event of a suspected anaphylactic reaction during study treatment infusion, the following procedures should be performed:

1. Stop the study treatment infusion.
2. Call for additional medical assistance.
3. Maintain an adequate airway.
4. Ensure that appropriate monitoring is in place, with continuous ECG and pulse oximetry monitoring if possible.
5. Administer antihistamines, epinephrine, or other medications and IV fluids as required by patient status and as directed by the physician in charge.
6. Continue to observe the patient and document observations.

## 1. **BACKGROUND**

Hemophilia A is an X-linked recessive bleeding disorder that occurs in approximately 1 in 5000 live male births. Patients with hemophilia A have a deficiency or absence of blood coagulation factor VIII (FVIII), an essential component of the intrinsic pathway in the coagulation cascade ([Mannucci and Tuddenham 2001](#); [Franchini and Mannucci 2013](#)).

The absence or functional deficiency of FVIII leads to a lifelong bleeding tendency. Common clinical signs of hemophilia A include easy bruising; prolonged bleeding after trauma or surgery; spontaneous bleeding into joints, muscles, or soft tissues; and intracranial hemorrhage. The severity of the disease roughly correlates with the residual endogenous level of FVIII activity. Approximately 68% of people with hemophilia A have moderate (25%) or severe (43%) forms, characterized by FVIII activity levels < 5% or < 1%, respectively, leading to frequent bleeding events with the sequelae of musculoskeletal complications (e.g., arthropathy), local functional deficits, hemorrhagic shock, neurocognitive defects, or even death ([World Federation of Hemophilia 2013](#)).

Prophylactic FVIII replacement therapy (i.e., administered on a scheduled basis with the intent to prevent bleeds) has been proven to minimize bleeding events and complications ([Manco-Johnson et al. 2007](#)). Since the 1990s, recombinant FVIII (rFVIII) concentrates have been standard-of-care treatment options for patients with hemophilia A ([Kingdon and Lundblad 2002](#)). Current prophylactic regimens commonly use infusion therapy administered three times weekly; other regimens use every other day administration ([Shapiro 2013](#)).

Prophylactic FVIII replacement therapy has been recognized as superior to episodic treatment of symptomatic bleeds for several decades ([Khawaji et al. 2012](#)) and was adopted by national and international organizations as the desired treatment approach. However, the burden of treatment ([Eton et al. 2013](#), [Mair and May 2014](#)) is extraordinarily onerous, as adequate prophylaxis requires a lifetime of self-administered intravenous (IV) infusion of FVIII 3–4 times each week. In addition to the obvious toll on the quality of patients' life ([Teal et al. 2014](#)), this burden results in suboptimal care for many who elect to avoid routine prophylaxis, despite its medical advantage ([Geraghty et al. 2006](#); [Lindvall et al. 2006](#); [De Moerloose et al. 2008](#); [Collins et al. 2014](#); [Oldenburg 2015](#)). Thus, episodic therapy is a standard-of-care for many patients with hemophilia in developed countries, where approximately one-third to one-half of the patients use FVIII on-demand and avoid continuous prophylaxis.

Emicizumab (also known as ACE910 and RO5534262) is a humanized monoclonal modified immunoglobulin G4 (IgG4) antibody with a bispecific antibody structure produced by recombinant DNA technology in Chinese hamster ovary (CHO) cells. Emicizumab bridges activated factor IX (FIXa) and factor X (FX) to restore the function of missing activated factor VIII (FVIIIa) that is needed for effective hemostasis. In

patients with hemophilia A, hemostasis can be restored irrespectively of the presence of FVIII inhibitors, as emicizumab shares no sequence homology with FVIII.

In addition, emicizumab offers the possibility of subcutaneous (SC) administration, removing the need for venous access. Finally, because the pharmacokinetic properties of this antibody are expected to enable marked extension of the dosing interval to once weekly, every other week, or even less frequently, this novel compound has the potential to dramatically change the treatment of patients with hemophilia A with or without FVIII inhibitors who are in need of effective, safe and low burden prophylactic therapy.

Initial experience with emicizumab in humans was generated from one Phase I study (ACE001JP) and its ongoing extension, a Phase I/II study (ACE002JP). See the RO5543262 [Emicizumab] Investigator's Brochure for additional details on clinical studies with emicizumab. The results have also been published ([Shima et al. 2016](#); [Uchida et al. 2016](#)). Based on these compelling data, the Phase III development program in adult and pediatric patients with hemophilia A (both with and without FVIII inhibitors) was initiated. Studies BH29884 (adults and adolescents) and BH29992 (pediatric) in hemophilia A patients with FVIII inhibitors had a first data readout at the end of 2016 when this study was already ongoing.

Consequently it was decided that a minimum of 40 patients with prophylactic FVIII replacement therapy should come from a separate non-interventional study (NIS; BH29768) and have at least 6 months of data in the NIS before enrolling into Arm D of Study BH30071 (see Section 2).

## **2. STUDY DESIGN**

Study BH30071 is a randomized, multicenter, open-label, Phase III clinical study will enroll patients aged 12 years or older with severe hemophilia A (intrinsic FVIII level < 1%)

without inhibitors against FVIII. Approximately 85 patients who received episodic treatment with FVIII prior to study entry and experience at least 5 bleeds over the prior 24 weeks (annual bleed rate [ABR]  $\geq 10$ ) will be randomized in a 2:2:1 ratio to the following regimens:

- Emicizumab prophylaxis at 3 mg/kg/week (wk) subcutaneously for 4 weeks, followed by 1.5 mg/kg/wk subcutaneously (Arm A)
- Emicizumab prophylaxis at 3 mg/kg/wk subcutaneously for 4 weeks, followed by 3 mg/kg/every 2 weeks (2wks) subcutaneously (Arm B), or
- No prophylaxis control arm (Arm C)

Randomization will be stratified according to the number of bleeds patients experienced over the last 24 weeks prior to study entry,  $<9$  versus  $\geq 9$  (or ABR 18), to ensure a balance of patients with lower versus higher number of bleeds in all arms. All patients will continue usual episodic treatment with FVIII in case of a breakthrough bleeding event.

[figure not shown]
In addition, 40–60 patients with severe hemophilia A who received FVIII prophylaxis prior to study entry will be enrolled and receive emicizumab prophylaxis at 3 mg/kg/wk subcutaneously for 4 weeks, followed by 1.5 mg/kg/wk subcutaneously (Arm D). To improve the validity of historical comparison in this group, at least 40 patients will be observed on FVIII prophylaxis in NIS BH29768 for a period of at least 24 weeks before enrolling in Arm D of this study.

The study schema is shown [Figure 1](#).

**Figure 1 Study Schema for Study BH30071**

## Phase III Non-Inhibitor Design

2wks = every 2 weeks; 6moBR = 6 months bleed rate; BR = bleed rate; FVIII = factor VIII; mo = month; R = randomization; wk = week.

a All patients will receive loading with four weekly doses of emicizumab 3 mg/kg/wk prior to starting maintenance.

[figure not shown]
b Arm C patients during the no prophylaxis period are designated Ccontrol; whereas, after switch to emicizumab (allowed per protocol after 24 weeks), they are designated Arm Cemi.

The primary efficacy analysis, defined as comparing the number of bleeds over time for patients randomized to receive prophylactic emicizumab versus no prophylaxis will be conducted after reaching the clinical cutoff, which occurs at the earliest timepoint when all randomized patients (Arms A, B, and C) and a minimum of 40 patients from Arm D have either completed 24 weeks in the study or discontinued from the study.

To obtain additional safety and efficacy data on emicizumab, patients who are randomized to the no prophylaxis arm (control arm, Arm Ccontrol) will have the opportunity to switch after 24 weeks to receive emicizumab prophylaxis at 3 mg/kg/2wks maintenance dose after 4 weeks of 3 mg/kg/wk loading dose. For clarity, Arm C patients during the no prophylaxis period are designated Ccontrol; whereas, after switch to emicizumab they are designated Arm Cemi. After completing at least 24 weeks of treatment with prophylactic emicizumab, patients who receive emicizumab prophylaxis (Arms A, B, D, or Arm Cemi after treatment switch) and derive clinical benefit will be allowed to continue emicizumab until marketing authorization as part of this study or a

separate extension study, as long as they continue to derive clinical benefit and emicizumab is still in clinical development.

Patients may be allowed to up-titrate their emicizumab dose if they meet the pre-specified criteria as described in the protocol. Patients in the randomized arms can escalate after at least 24 weeks on emicizumab prophylaxis, while dose increase is permitted at any time after the second qualifying bleed for patients in Arm D.

## **2.1            PROTOCOL SYNOPSIS**

The protocol synopsis is in [Appendix 1](#).

## **2.2            COLLECTION OF PATIENT-REPORTED DATA**

### **2.2.1            Collection of Bleed and Medication Data**

Bleed and medication data are collected through an electronic bleed and medication questionnaire (BMQ), which was developed by the Sponsor given that no standard questionnaire for collection of these data exists.

The BMQ was developed as a patient-reported measure of bleeding episodes (including cause, type, location, and symptoms of bleeds) and hemophilia-related medication use. The draft questions were developed following review of the hemophilia A literature and discussions with medical professionals regarding what information on related bleeds was most important to capture. Prior to use in this study, qualitative interviews with patients with hemophilia A were conducted in order to evaluate the measure's content validity and to test the understanding and usability of the BMQ on an electronic, handheld device. Cognitive interviews were conducted in person with a total of 20 patients aged 12 years and older with hemophilia A; the results demonstrated that the BMQ was comprehensive and relevant to patients' experiences with bleeds and treatments.

To capture bleed data, emicizumab use, and other hemophilia medication use during study treatment, patients will complete the BMQ on a handheld device that will be provided to them during the Week 1 visit at the study site. This device will remain with the patient for the duration of the study to enter bleed and medication data weekly at a minimum. In case a patient did not experience any bleeds or administer any treatments for a week, the patient is asked to log into the device and fill in the questionnaire to confirm this. These weekly entries, in addition to the bleeds and medication entries, can also be used to assess compliance. Of note, the patient is able to enter bleeds and medications for the past 8 days, including the day the entries are made. This retrospective data entry window was considered acceptable in terms of recall bias and was added in order to optimize the completeness of data collection.

Patients who withdraw from emicizumab treatment will continue to record bleeds and hemophilia medication administration until they complete the safety follow-up visit.

The patient is able to edit and delete bleeds and medications for 24 hours after they are entered. Furthermore, the investigator and patient are instructed to review the data together at every clinic visit. If the patient has been unable to enter data for any reason, the investigator is able to do so using a data clarification request (DCR; not subject to the previous 8-day data entry window). Note, the symptoms of joint and muscle bleeds are not collected in this case because the patient may not be able to reliably remember them. In addition, the investigator is able to request a change be made to the vendor's database by submitting a DCR.

Furthermore, the Sponsor's data manager and Medical Monitor review the patient entered data for clear inconsistencies against data collected on the electronic Case Report Form (eCRF) or to identify obvious data points to be clarified (e.g., missing entry of the weekly emicizumab injection). These requests are sent to the investigator, who reviews them with the patient and may enter the data via the site data entry system or request a change to be made in the vendor's database via a DCR, if necessary.

### **2.2.2 Collection of Health-Related Quality-of-Life Data**

At specified visits, patients will complete health-related quality-of-life (HRQoL), health status, and satisfaction/preference questionnaires on a tablet device that will remain at study sites. The instructions for completing the patient-reported outcome (PRO) questionnaires electronically will be provided by the investigator staff during the Week 1 visit at the site. The data will be transmitted automatically after entry to a centralized secure database at the vendor.

### **2.2.3**

[REDACTED]

[REDACTED]

[REDACTED]

[REDACTED]

[REDACTED]

[REDACTED]

## **2.3 ENDPOINTS**

### **2.3.1 Primary Efficacy Endpoint**

Bleed rate is defined as the number of bleeds over the efficacy period. A bleed is counted in the primary analysis if it was treated with coagulation factors and fulfills the adapted International Society on Thrombosis and Haemostasis (ISTH; [Blanchette et al. 2014](#)) criteria, as described in Section 4.5.8 of the protocol. More specifically, the following rules as outlined in the sections below are applied.

#### **2.3.1.1 Efficacy Period**

The start of the efficacy period for each individual patient is defined as the first day when there is data in the BMQ. For patients starting the study on emicizumab (Arms A, B, and D) this is expected to coincide with the Week 1 visit, and the day of their first emicizumab dose. For patients who do not start the study on emicizumab (Arm C), the start of the efficacy period should coincide with the Week 1 visit.

Of note, the first day when there is data in the BMQ, includes the first day for which data is reported via the handheld device, a DCR, or the day of device activation.

A second efficacy period is defined for patients in Arm C who switch to emicizumab starting on the day of their first emicizumab dose.

For patients randomized or enrolled on emicizumab, the end of the efficacy period is defined as the date of the clinical cutoff or the date of withdrawal from the initial study period (i.e., treatment phase according to eCRF), whichever is earlier. For patients randomized to no prophylaxis (Arm C), the end of the first efficacy period is defined as the day before the first emicizumab dose or the date of withdrawal from the initial study period (i.e., treatment phase according to eCRF) or the date of the clinical cutoff if

neither of the aforementioned events has taken place. For patients whose dose is up-titrated, the efficacy period on the initial dose (the initial period for patients randomized/enrolled to Arms A, B, and D; the second efficacy period, starting at first emicizumab dose for patients randomized to Arm C) ends 1 day prior to the first day on the up-titrated dose.

For patients who withdraw from the study before reaching the Week 1 visit, the duration of the efficacy period is set to 1 day, and it starts and ends on the day of randomization/enrollment.

For patients whose dose is up-titrated, the bleeds on the up-titrated dose are analyzed separately. The efficacy period on a given up-titrated dose (second efficacy period for patients randomized/enrolled to Arms A, B, and D; third efficacy period for patient randomized to Arm C) starts with the first day on this dose and ends on the day of the clinical cutoff or the date of withdrawal.

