To avoid bleeds before adequate emicizumab plasma concentration is reached, these patients will continue their regular FVIII prophylaxis until the second emicizumab loading dose. At the end of the first week of treatment, 95% of patients are expected to achieve emicizumab level of 8 µg/mL, which is projected to have FVIII activity equivalent to approximately >2%. Thrombotic events were not found in the Japanese Phase I/II study where doses of FVIII were administered to treat breakthrough bleeds while patients had higher emicizumab steady-state level, supporting the safety of this approach. Importantly, routine prophylaxis will be prohibited for all patients enrolled in Arms A, B, or C and for patients in Arm D immediately after the second emicizumab dose.

Study enrollment will take place at the Week 1 visit. A patient who fulfills the inclusion and exclusion criteria should be enrolled and assigned to a treatment arm at the Week 1 visit, the same day when the first dose of emicizumab is due for patients in Arms A, B, and D.

[figure not shown]
Emicizumab is intended for prophylactic use only (i.e., not to treat bleeds that have already occurred). The primary efficacy analysis, defined as comparing the number of bleeds over time for patients randomized to receive prophylactic emicizumab versus no prophylaxis will be conducted at the earliest timepoint when all randomized patients (Arms A, B, or C) and a minimum of 40 patients from Arm D have either completed 24 weeks in the study or discontinued from the study. Therefore, there will be a range of observation periods from 6 to approximately 12 months, or longer. Study patients will be enrolled globally from the Americas, Europe, Africa, and Asia-Pacific region.

To obtain additional safety and efficacy data on emicizumab, patients who are randomized to the no prophylaxis arm (control arm, Arm C) will be expected to switch after 24 weeks to receive emicizumab prophylaxis at 3 mg/kg/2wks maintenance dose after 4 weeks of 3 mg/kg/wk loading dose. This dose was chosen to enhance the safety and efficacy data obtained with Arm B patients.

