4.4.2 Prohibited Therapy

Use of the following therapies is prohibited during the study and for at least 4 weeks prior to initiation of study treatment:

- Drugs that would affect hemostasis (e.g., aspirin, non-steroidal anti-inflammatory drugs that are not selective or preferential COX-2 inhibitors, or anticoagulants [other than to flush, dwell, or de-clot a venous access device])

Drugs intended to control bleeding episodes or used in the context of minor surgery (e.g., tooth extraction) or injuries (e.g., concussion) to prevent deterioration or given if deemed medically necessary for management of certain conditions (e.g., post cardiac surgery) are permitted.

- Use of systemic immunomodulators (e.g., interferon) other than anti-retroviral therapy
- Elective surgery (excluding minor procedures such as tooth extraction, CVAD removal, or incision and drainage as well as emergency surgeries)
- Use of other investigational drugs

Use of concomitant prophylactic regimen is prohibited during the study, except for patients on Arm D who will continue FVIII prophylaxis until the Week 2 dose. (Short-term prophylaxis [e.g., around the time of surgery], however, is permitted.)

If prohibited therapy is administered for any reason, it should be recorded on the eCRF (except any hemophilia-related medication, which will be recorded on the Bleed/Medication Questionnaire). If prohibited treatment is prescribed or considered

medically necessary, the medical monitor should be consulted to discuss any changes in the benefit/risk and determine whether the patient should continue on the study.

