Appendix 1 Schedule of Assessments (cont.)

-
- ⁱ Concomitant medications (e.g., extra pain medication with bleed) will be asked about at the time of the monthly assessment, excluding treatments for bleeds (i.e., FVIII and other medications to treat bleeds), which will be collected on the bleeding questionnaire. Hemostatic medications to treat or prevent bleeds in the week prior to starting emicizumab will also be collected and during Week 1 for patients in Arm D who continue their prior FVIII prophylaxis for the first week of the study.
- ^j Performed locally. If screening ECG is abnormal, repeat at Week 1 (or Week 2 [or Week 5 for Arm C] if Screening and Week 1 occur on the same day), otherwise do not repeat. ECGs will also be performed 4–8 and 24 weeks after starting emicizumab or dose escalation (up-titration), as well as at study completion/early termination.
- ^k Patient must have a documented local inhibitor test with negative result (<0.6 BU) at screening or within the 8 weeks prior to enrollment. Starting at Week 1, all subsequent anti-FVIII antibodies will be measured at a central laboratory using an aliquot of the citrate plasma collected for PD biomarker assessments, so a separate blood draw is not necessary. Please consult the central laboratory services manual for details.
- ^l Samples to detect anti-emicizumab antibodies will be collected prior to emicizumab administration at every clinic visit. However, only samples from the following visits will be analyzed initially: (Arms A, B, and D) immediately prior to the first injection at Week 1, every 8 weeks from Weeks 9–49, every 12 weeks starting from Week 61, and at the 24-week post-emicizumab safety follow-up visit following initiation of emicizumab; Arm C immediately prior to the first injection at Week 25, every 8 weeks from Weeks 33–73, every 12 weeks starting from Week 85, and at the 24-week post-emicizumab safety follow-up visit following initiation of emicizumab. If any of these samples are positive and/or if there is suboptimal clinical response or low pharmacokinetic exposure, the remaining collected samples may be analyzed for anti-emicizumab antibodies. Anti-emicizumab antibodies may also be drawn at the time of systemic hypersensitivity events.

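### SAP 2.3.1.1 ties the start of the efficacy period to the first diary day with no cut-off at Week 1, so bleeds and days from before randomisation or first dose can enter the bleed endpoints

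*SAP*

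**What the plan says.** The operative rule is in SAP 2.3.1.1: "The start of the efficacy period for each individual patient is defined as the first day when there is data in the BMQ". A note adds that this "includes the first day for which data is reported via the handheld device, a DCR, or the day of device activation". For reported data, the date that counts is the date the entry describes, not the date on which it was made.

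The link to the Week 1 visit is only an expectation. For Arms A, B and D, "this is expected to coincide with the Week 1 visit, and the day of their first emicizumab dose". For Arm C, "the start of the efficacy period should coincide with the Week 1 visit". Neither sentence says what to do when the dates differ.

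SAP 2.2.1 issues the device at the Week 1 visit and says that "the patient is able to enter bleeds and medications for the past 8 days, including the day the entries are made". Investigator entries through a data clarification request (DCR) are exempt from that window.

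Under Protocol 3.1 an eligible patient "should be enrolled and assigned to a treatment arm at the Week 1 visit", which is also the day of first dose in Arms A, B and D. SAP 4.5.1 uses the length of the efficacy period as the offset in the negative binomial model, and SAP 2.3.2 applies the same period to every bleed-related secondary endpoint.

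**The concern.** A start date set by a diary entry can depend on the outcome. If a bleed from before Week 1 is entered, that bleed can open the period and is then counted in it. The trial is open-label and the device is handed over on the day the arm becomes known, so these entries are made with knowledge of the assignment.

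The SAP fixes its other period starts by date. Arm C's second period starts at the first dose, an up-titrated period starts on the first day at the new dose, and patients who withdraw before Week 1 get one day at randomisation or enrolment. Only the main start floats. The sensitivity analysis limited to the first 24 weeks (SAP 4.5.4) takes the same start, so it does not remove early data.

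In Arm D, any back-entered days would be time on prior FVIII prophylaxis counted as emicizumab time. The non-interventional study period can end as late as one day before enrolment (SAP 2.3.2.5), so such days could fall in both periods of the intra-patient comparison.

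**Working it through.** **1. The rule applied to one patient.** At the Week 1 visit a patient enters a bleed from 5 days earlier, treated with FVIII. The first day with data is day −5. The period starts there, the bleed counts as a treated bleed, and the offset is 5 days longer. No other SAP rule reverses this.

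**2. The plan's own figures.** Protocol 6.1 and SAP 2.4 assume ABRs of 4 and 14, variance 10 times the mean, 30 versus 15 patients, 0.5 years of follow-up and two-sided 0.05.
- Rate ratio: 4/14 = 0.286.
- Dispersion, k = (variance − mean)/mean²: (40 − 4)/16 = 2.25 and (140 − 14)/196 = 0.643.
- SE² of the log rate ratio: (1/(4×0.5) + 2.25)/30 + (1/(14×0.5) + 0.643)/15 = 0.0917 + 0.0524 = 0.144, so SE = 0.380.
- ln(14/4)/0.380 − 1.96 ≈ 1.34, which gives power of 91.0%. This matches the stated figure of more than 90%. With 34 versus 17 it is 94.0%.

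**3. Illustration: seven full days enter one emicizumab arm.** The 7 days come from the 8-day window less the day of entry. The pre-dose rate is taken as 5 per 24 weeks (the entry minimum) to 9 per 24 weeks (the stratum cut).
- Extra bleeds in one week: 5/24 = 0.208 to 9/24 = 0.375.
- Expected bleeds over 24 weeks at ABR 4: 4 × 168/365.25 = 1.84.
- New ABR: (1.84 + 0.208)/(175/365.25) = 4.27, to (1.84 + 0.375)/(175/365.25) = 4.62.
- Rate ratio: 4.27/14 = 0.305 to 4.62/14 = 0.330.
- If the 7 days hold medication entries but no bleeds: 1.84/(175/365.25) = 3.84, and 3.84/14 = 0.274.

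**4. Second mechanism: the first reported bleed sets the start.** Here the bleeds enter with little added time. The assumptions are a pre-dose ABR of 14, all pre-dose bleeds in the 7 days reported, 168 days on treatment, and the emicizumab arm only. Simulation gives 0.27 extra bleeds per patient, 22% of patients with at least one, and a mean extension of 0.93 days.
- ABR: (1.84 + 0.27)/(168.93/365.25) ≈ 4.56; rate ratio 0.326.
- Pre-dose ABR of 10 or 30 instead of 14: 0.314 or 0.371.
- Half of the bleeds reported: 0.306.
- 365 days on treatment: 0.304.
- The same contamination in Arm C (control ABR 14.51): 4.56/14.51 = 0.314.

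**5. Power under mechanism 4.** In 1,500 simulated negative binomial regressions per setting, with pre-dose bleeds drawn independently of on-treatment bleeds, power falls from 90.0% to 87.4% (30 versus 15) and from 92.4% to 90.8% (34 versus 17).

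**The case against.** The best defence is that the SAP plainly intends a Week 1 start. The device is issued and patients are trained that day, the diary is described as capturing data during study treatment, and the sponsor's data manager and Medical Monitor check entries for inconsistencies. The number of pre-Week 1 dates could be nil. Where bleeds do enter, the error runs mostly against emicizumab, so it does not flatter the primary claim. All of that stands. It bears on the size of the problem and leaves the missing cut-off in place.

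A reader might go further in three ways that the documents do not support.

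- **That the problem falls mainly on the emicizumab arms.** Protocol Appendix 1, footnote i, says "Hemostatic medications to treat or prevent bleeds in the week prior to starting emicizumab will also be collected". That week lies before Week 1 in Arms A, B and D but inside Arm C's control period. The footnote sits in the concomitant-medication row, however, and names no form for these records. The statement in Protocol 4.4.2 about "any hemophilia-related medication, which will be recorded on the Bleed/Medication Questionnaire" concerns prohibited therapy. The 8-day window and the DCR route are open to Arm C as well, so a difference between arms is only an inference.
- **That the rule also loses bleeds after randomisation.** Device activation counts as data, and a recorded bleed sets the start by its own date. Only event-free days before a late activation can drop out.
- **That nearly every Arm D patient would have prior-week infusions in this diary.** No passage says so. At least 40 of the 40 to 60 Arm D patients come from the non-interventional study, whose own diary covers time until shortly before enrolment.

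**Conclusion.** The concern holds as a gap in the period definition. As written, SAP 2.3.1.1 lets bleeds and days from before randomisation or first dose into both the count and the offset, in any arm, and lets a reported bleed set its own patient's start date.

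The likely effect is small. On the one-week illustration the planned rate ratio moves from 0.286 to about 0.305 to 0.330, mostly against emicizumab; medication-only days would pull it to 0.274. These figures rest on an assumed pre-dose bleed rate, a 7-day limit, and entry in an emicizumab arm alone. They might be read as an upper bound, but they are not one: the upper stratum has no ceiling, DCR entries can reach back further, and the bleed-triggered scenario reaches 0.371 at a pre-dose ABR of 30. The share of patients affected, and whether it differs by arm, is not in the documents.

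The case for changing the rule does not depend on a difference between arms. An outcome-dependent start is undesirable in itself, and equal contamination of both arms still moves the ratio to 0.314 on the stated assumptions.

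**What to change.** In SAP 2.3.1.1:

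- Do not let the efficacy period start before the day of randomisation (Week 1 visit) for Arms A, B and C, or before the first emicizumab dose for Arm D. Exclude bleeds with onset before that date from all endpoint counts.
- Where the device was activated late, count the days from Week 1 as exposure only if bleed data for them were captured by handheld back-entry or DCR. Starting at randomisation regardless would add days to the offset as bleed-free time when nobody was recording bleeds.
- State that a later bleed linked by the 72-hour rule to an excluded pre-start bleed is not counted as a new bleed.
- Report, by arm, the number of patients with diary dates before Week 1.

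Leave the start of Arm C's second period at the first dose, as it is. The cost is a few sentences in the SAP, one changed derivation and one added count, with no new data.
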